1.2 Key Roles and Study Governance

Sponsor	Medical Director
N/A, principal investigator-initiated study	[name]
	Division of Thoracic Surgery, Hospital of the University of Pennsylvania
	[name]
	[contact]
	[contact]

- 1.3 Schema

Office (within 1-30 days prior to surgery) - Informed Consent

- Obtain informed consent alongside surgery consent
- (Optional) Obtain patient or family member email address (linked to their Apple ID) to approve access to the Airalux app on their App Store (IOS only)
 - The Airalux app provides guided IS exercise sessions, allows patients and family members to view past IS exercise measurements, and gamifies adherence metrics.

Pulmonary function lab – Spirometry Testing

- Patients will receive spirometry testing at the pulmonary function lab. This is part of routine care. This is not a study intervention.

Pre-op holding (morning of surgery) - Baseline Measurement

- Patients receive the Airalux device and use it to perform a baseline IS measurement
- Research team records the device identification key of the device that the patient is receiving
- (Optional) For patients with the Airalux app, they can sign in to the app with their device identification key.

Post-anesthesia care unit (2-4 hours post-surgery) - Study Intervention Administered

- Patients are instructed to perform IS exercises with their device
- The device will gently vibrate/buzz every 15 minutes to prompt patients to complete an IS exercise
- (Optional) Patients can follow guided exercises on the app if desired

Inpatient hospital floor (0-7 days post-surgery) - Study Intervention Administered, Collection of Endpoints

- Patients are instructed to perform IS exercises with their device throughout their hospital stay
- The device will vibrate every 15 minutes to prompt patients to complete IS exercise
- (Optional) Patients can follow guided exercises on the app if desired
- Patient pulse oximetry data is collected every 4 hours. This is part of routine care. This is not a study intervention.
- Patient pain scores are collected at minimum every 12 hours (at least once per shift). This is part of routine care. This is not a study intervention.

Discharge - Study Ends (conclusion of hospital stay)

- Patients will not be able to use the Airalux device outside of the hospital
- Patients will receive a standard of care incentive spirometer to use at home

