7 STUDY INTERVENTION DISCONTINUATION AND PARTICIPANT DISCONTINUATION/WITHDRAWAL

7.1 Discontinuation of Study Intervention

Discontinuation from protocol specified activities will result in discontinuation from the study. In this situation, the device is the only clinical intervention being utilized with patients. As such, discontinuing the use of the IS device prohibits data collection and renders the patient's data incomplete and therefore useless for analyses. Furthermore, there are no follow ups involved in this study so discontinuation from device intervention prevents collection of metrics associated with secondary endpoints and constitutes a patient's discontinuation from the study.

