8 STUDY ASSESSMENT AND PROCEDURES

8.1 Efficacy Assessments

Study Procedures and Evaluations:

- 1) Patient identification and eligibility screening:
 - a. Once a potential participant is identified as already scheduled for a lung resection surgery, the clinical team will determine whether the patient satisfies the eligibility criteria.
 - b. Any additional eligibility criteria that cannot be identified or evaluated via Penn Charts will be reviewed and confirmed by the clinical team following receipt of signed ICF forms.
- 2) Patient visit and informed consent:
 - a. If any additional eligibility criteria need to be screened due to a lack of information in Penn Charts, the patient will be asked relevant questions after providing necessary informed consent to the clinical team.
 - i. This will take place in the doctor's office that is private. Note that in-patient hospital stay will not be billed to the study as the hospital stay is unrelated to participation in the study.
- 3) Patient spirometry testing at the pulmonary function laboratory
 - a. This is already done as part of routine care. This is not a study intervention. Lab results from spirometry testing will be a secondary endpoint.
- 4) Device intervention during patient visit
 - a. After receiving informed consent, during preoperative holding, the clinical team will give the patient one digital IS, facilitate the download of the companion app onto the patient's personal mobile device if applicable, and obtain a baseline inspiratory volume measurement.
 - b. Post-surgery, the clinical team will teach patients how to perform breathing exercises with the digital IS and instruct them regarding the quantity, frequency, and volume of inspiratory breaths to perform throughout their hospital stay.
 - i. While the digital IS is powered on, an auditory and haptic reminder will occur every 15 minutes to remind the patient to perform their breathing exercises. The patient has full autonomy as to when and how often to use the digital IS. Digital IS usage and inspiratory volume data will be collected by the device whenever it is used by the patient.
 - ii. At minimum twice per day, the clinical team will collect pain scores. This is already done as part of routine care. This is not a study intervention.

- iii. Every 4 hours, the clinical team will record a patient's SpO2. This is already done as part of routine care. This is not a study intervention.

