- c. At discharge, patients will complete a short survey on their experience with the device and IS performance.
- d. Use of the digital IS, and the resulting analysis on adherence, are the primary outcome of this clinical study. Metrics relating to lung function, including inspiratory volume measures, SpO2, pulmonary function lab testing, and pain scores, are the secondary outcomes of this clinical study.
- e. No other vital sign data will be obtained for the study. No follow-up visits will occur. Any withdrawal from the study will occur during this visit as it is the only visit.

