10.1.8 Data Handling and Record Keeping

10.1.8.1 Data Collection and Management Responsibilities

Data collection is the responsibility of the study team under the supervision of the principal investigator. The investigator is responsible for ensuring the accuracy, completeness, legibility, and timeliness of the data reported.

All source documents should be completed in a neat, legible manner to ensure accurate interpretation of data and follow ALCOAC standards (attributable, legible, contemporaneous, original, accurate, and complete). If any responses are illegible, the PI or member of the study team must ask the patient to clarify that response verbally. Inspiratory breath data will be recorded by the digital IS devices and transferred via HUP or PPMC's WiFi network to a secure cloud-based database for research use. Patient blood saturation, pulse oximetry, age, weight, height, sex at birth, and pulmonary function lab spirometry results will be recorded on a computer linked and managed by the Hospital of the University of Pennsylvania and Penn Presbyterian Medical Center, and then data will be obtained from EPIC and transferred via the cloud-based database or PennBox for research use. This computer will be located on the floor where all patients enrolled in the study will be managed post-operatively.

Hardcopies of the consent forms will be scanned, stored and maintained at Penn Presbyterian Medical Center in room 245B. Data recorded in the data collection software derived from source documents should be consistent with the data recorded on the source documents. Patient participation in the study will not be recorded in the EMR.

Regarding data processing, any and all listed study members may be involved in data processing (i.e., statistical analysis) as data will not contain patient names at this point in the analysis.

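### Section 7.1 wrongly says that stopping the device prevents secondary-endpoint collection; applied as written, it drops formal stoppers from the SpO2, pain and survey results and conflicts with section 9.4.3

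*Combined protocol and SAP*

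**What the plan says.** Section 7.1 makes three linked statements:

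- On study status: "Discontinuation from protocol specified activities will result in discontinuation from the study".
- On analysis: stopping the device "renders the patient's data incomplete and therefore useless for analyses".
- On the reason: there is no follow-up, so "discontinuation from device intervention prevents collection of metrics associated with secondary endpoints".

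Section 3 lists four secondary endpoints: postoperative SpO2, postoperative pain, preoperative pulmonary function results and postoperative breath quality (volume and flow). The discharge survey is tertiary.

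Other sections say where these data come from:

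- SpO2, section 1.3: "Patient pulse oximetry data is collected every 4 hours. This is part of routine care. This is not a study intervention". Section 8.1 agrees: "Every 4 hours, the clinical team will record a patient's SpO2. This is already done as part of routine care".
- Pain, section 8.1: "At minimum twice per day, the clinical team will collect pain scores". This too is described as routine care.
- Route, section 10.1.8.1: for SpO2 and pulmonary function, "data will be obtained from EPIC and transferred via the cloud-based database or PennBox for research use". Section 10.1.3 places pain scores on hospital computers as well.
- Survey, section 8.1: "At discharge, patients will complete a short survey on their experience with the device and IS performance".

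Section 7.2 lets the investigator withdraw a participant who will use only the ordinary spirometer, or who newly meets an exclusion criterion. Anyone who leaves after receiving the device is not replaced. Section 9.3 defines the analysis population only as adults, and section 9.4.3 summarises the secondary endpoints over the whole patient population.

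**The concern.** The stated reason for ending data collection does not match the protocol's own procedures. A patient who puts the device down remains in hospital, where SpO2 and pain continue to be charted. Ending participation at that moment discards data that would exist anyway and need no study procedure.

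The loss is unlikely to be random. One listed route out is preferring the ordinary spirometer, which is itself a judgement on the device, yet that patient leaves before the user-experience survey. The other is a newly met exclusion criterion, and exclusion 3 in section 5.2 covers patients for whom spirometry has become medically inappropriate. With 30 patients and purely descriptive summaries, a few such losses could change what the SpO2, pain and survey results describe.

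This is separate from how stoppers' adherence data are counted. Settling that question would not recover their SpO2, pain or survey data.

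**Working it through.** **Step 1: does each endpoint need the device?** The plan gives no figure to reproduce here, so the check is of sources.

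| Endpoint | Source | Ends when the device stops? |
|---|---|---|
| SpO2 | Routine care, every 4 hours (1.3, 8.1); EPIC (10.1.8.1) | No |
| Pain | Routine care, at least twice daily (8.1); hospital computers (10.1.3) | No |
| Pulmonary function | Preoperative laboratory (1.3, 3) | No, already obtained |
| Breath volume and flow | Device sensor | Yes |
| Survey (tertiary) | Asked at discharge (8.1) | No, but lost if the patient has left the study |

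The 7.1 statement is therefore correct for one of four secondary endpoints. Its sentence on secondary metrics does not cover the survey. The survey is lost only because 7.1 ends participation before discharge.

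**Step 2: loss within one stopper.** Inputs are an average stay of 2-3 days (section 1.1), SpO2 every 4 hours and at least 2 pain scores a day. The stop at 24 hours is an assumption.

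- SpO2 readings over the stay = hours / 4: 48/4 = 12, or 72/4 = 18. Before the stop: 24/4 = 6. Lost: 6/12 = 50%, or 12/18 = 67%.
- Minimum pain scores = 2 × days: 4 or 6. Before the stop: 2. Lost: 2/4 = 50%, or 4/6 = 67%.
- If the patient's data are treated as unusable, as 7.1 says, the earlier readings go too: 12/12 or 18/18 = 100%, and likewise for pain.

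**Step 3: effect on the study summary if stoppers are dropped entirely.** The documents give no stopping rate and no difference between stoppers and continuers, so both are assumed. With k of 30 stopping, the mean in continuers differs from the mean in all recipients by (k/30) × gap. The standard error is multiplied by √(30/(30 − k)), assuming a common SD.

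| k | Patients left | Shift, gap 0.5 SD | Shift, gap 1 SD | SE ratio |
|---|---|---|---|---|
| 3 | 27 | 0.05 SD | 0.10 SD | 1.054 |
| 6 | 24 | 0.10 SD | 0.20 SD | 1.118 |
| 9 | 21 | 0.15 SD | 0.30 SD | 1.195 |

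The formula gives a size for an assumed gap. It does not say which way the gap runs.

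**Step 4: 7.1 against section 9.** A summary over the whole population cannot be produced if 7.1 stops collection and rejects the data of some recipients. Section 9.4.2, for the primary endpoints, excludes affected days and not patients. No section says which rule governs stoppers for the secondary endpoints.

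**The case against.** A reader might infer that the SpO2, pain and survey results will come only from continuing users, and so will make recovery and satisfaction look better than they were. The documents do not support that as a settled fact. Section 9.4.3 points to all patients, so restriction to continuers is what 7.1 implies and not a fixed analysis rule. Nor is the direction known: patients may stop because they are unwell, because they feel well, or because they prefer the ordinary device. No survey analysis is specified, so an inflated satisfaction percentage cannot be derived.

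The affected group is also narrow. Section 8.1 leaves timing and amount of use to the patient, so someone who uses the device little stays enrolled and is surveyed. Section 6.2.1 replaces devices that fail. The issue concerns formal stopping or withdrawal only.

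Finally, the secondary objective concerns patients using the digital device, so readings after a switch to another spirometer arguably answer a different question. The study is exploratory, with no hypotheses and only means and SDs planned.

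All of this stands and limits the point. It does not rescue the sentence in 7.1, which is wrong about how SpO2, pain and pulmonary function are obtained. The objective's wording is a reason to show on-device readings separately, not to leave the rest uncollected.

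**Conclusion.** The point holds as an internal contradiction with a real but unquantified consequence. Section 7.1 is wrong for SpO2, pain and preoperative pulmonary function, right for device-measured volume and flow, and unreconciled with sections 9.3 and 9.4.3. Followed literally, it removes formal stoppers selectively and without replacement from the SpO2 and pain summaries, and from the survey.

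Per stopper, the loss is 50-67% of SpO2 readings and minimum pain scores if earlier readings are kept, and 100% if they are discarded. The partial figures rest on the assumed stop at 24 hours and the documented 2-3 day average stay. The shifts of 0.05 to 0.30 SD are illustrations under assumed stopping rates and gaps. An upward bias in recovery or satisfaction is possible but is not established by the documents.

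**What to change.** - In 7.1, delete the statements that stopping the device prevents secondary collection and that the patient's data cannot be used. State that only device-measured volume and flow cease.
- Define stopping the device and withdrawing consent as separate events. Withdrawal of consent for data use stays under section 10.1.4.
- For patients who only stop the device, continue extracting routine SpO2 and pain to discharge or the 1-week limit, retain the pulmonary function results, and give the existing survey at stopping or at discharge.
- Reconcile 7.1 with 9.3 and 9.4.3: report these endpoints in all device recipients, with the number of stoppers and their reasons (section 7.2 already has reasons recorded). Show stoppers separately, or add a summary of on-device readings only, to respect the wording of the secondary objective.

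The cost is protocol wording, possibly consent wording, and a few more chart extractions. No new measurement or procedure is added, and clinical care does not change.

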7.2 Participant Discontinuation/Withdrawal from the Study

Participants are free to withdraw from participation in the study at any time upon request.

An investigator may discontinue or withdraw a participant from the study for the following reasons:

- If the participant meets any of the exclusion criteria (either newly developed or not previously recognized) that precludes further study participation.
- If the participant insists on using the standard of care IS device.

The reason for participant discontinuation or withdrawal from the study will be recorded by the study team. Given that none of the aforementioned reasons constitutes an adverse event, it may be the case that no further reporting is necessary. Subjects who sign the informed consent form but do not receive the digital IS may be replaced. Subjects who sign the informed consent form and receive the digital IS, and subsequently withdraw, or are withdrawn or discontinued from the study, will not be replaced.

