4 STUDY PLAN

4.1 Study Design

We hypothesize that use of the investigational device will have a positive impact on patient incentive spirometry adherence. This is a single-arm, exploratory study that will be conducted at the Hospital of the University of Pennsylvania (HUP) and Penn Presbyterian Medical Center (PPMC). The digital IS utilizes a sensor to measure inspiratory breath volume and flow rates, and this data, as well as the time stamps, are transmitted wirelessly to a secure cloud database and a companion mobile-based app. The IS and app incorporate features to instruct and remind patients about their exercises, which include auditory and visual cues as well as a gentle auditory and haptic reminder to perform exercises. Furthermore, the app has additional features to encourage breathing exercises in the form of gamification strategies, and separate interfaces for patients and medical staff to monitor device usage. All of the features are aimed at improving patients' adherence to incentive spirometry.

Subjects will be recruited from patients undergoing any lung resection surgery performed by [name], [name], and/or [name] at HUP and/or PPMC and for which an incentive spirometer is expected to be used by the patient after their surgery. The target enrollment for the study is 30 subjects. The duration of the subject's participation with the trial will be for their entire postoperative hospital stay up to 1 week postoperatively. At the beginning of the subject's participation, study activities will be focused on informed consent, instruction on use of the digital IS, and obtaining baseline inspiratory volume measurements. Most of the remainder of the subject's participation time will be focused on passive data collection performed by the digital IS.

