5.2 Exclusion Criteria

There are no exclusions based on economic status, gender, race, or ethnicity. An individual who meets any of the following criteria will be excluded from participation in this study:

1. Vulnerable populations who in the opinion of the investigator are unable to give Informed Consent for reasons of incapacity, immaturity, adverse personal circumstances or lack of autonomy.
2. History of prior non-compliance to prescribed therapy or presence or history of significant psychiatric condition (e.g., drug or alcohol addiction, psychosis, schizophrenia), or cognitive issue which would in the opinion of the investigator, make it difficult for the patient to comply with the study procedures or follow the investigators instructions.
3. Populations for whom in the opinion of the investigator, incentive spirometry is deemed inappropriate due to medical condition or otherwise.
4. Pregnant individuals due to low likelihood of meeting inclusion criteria 4 in section 5.1.

Licensed medical professionals on the clinical team will follow proper procedures in determining if the individual is consenting. Proper procedures entail doing all of the following: giving a patient adequate information concerning the study, providing adequate opportunity for the patient to consider all options, responding to the patient's questions, ensuring that the patient has comprehended this information, obtaining the patient's voluntary agreement to participate and, continuing to provide information as the patient or situation requires. There will be ample opportunity for the patient to ask questions. In the event that the patient is in a vulnerable population and unable to provide consent, they will not be eligible to participate in the study and thus will not be screened. If the individual is not able to provide informed consent or if consent is not certain due to impairments or other factors, they will not be considered for study participation. In the event that the patient is in a vulnerable population and unable to provide consent, they will not be eligible to participate in the study and thus will not be screened.

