6.3 Measures to Minimize Bias: Randomization and Blinding

This is a single-arm exploratory study which will not require participant randomization or blinding.

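### Section 7.2 permits investigator withdrawals related to device use, and Section 7.1 then discards those patients' data, which could bias both primary means upward

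*Combined protocol and SAP*

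**What the plan says.** Section 7.2 gives two reasons for which an investigator may withdraw a participant. The first is "If the participant meets any of the exclusion criteria (either newly developed or not previously recognized) that precludes further study participation". The second is "If the participant insists on using the standard of care IS device". The reason must be recorded, and patients who have received the device are not replaced.

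The first reason brings in every criterion of Section 5.2. Exclusion 2 begins "History of prior non-compliance to prescribed therapy or presence or history of significant psychiatric condition" and goes on to a "cognitive issue which would in the opinion of the investigator, make it difficult for the patient to comply with the study procedures".

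Four other places bear on the point:

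- Section 4.1 says that the app has "separate interfaces for patients and medical staff to monitor device usage", and Section 6.3 states "This is a single-arm exploratory study which will not require participant randomization or blinding".
- Section 8.1 says: "The patient has full autonomy as to when and how often to use the digital IS".
- Section 7.1 says that stopping the device leaves the patient's data incomplete and of no use for analysis.
- Section 9.3 describes the analysis population only as adult patients. Section 9.4.2 reports the mean and SD of each primary endpoint, with no comparator.

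**The concern.** A rule on compliance is ordinary at enrolment, before any outcome exists. Applied again during the stay, it operates while the outcome is accruing. The primary endpoints are breath attempts per day and the percentage of recorded hours with at least one attempt, so complying with the main study procedure and scoring well on the endpoints are nearly the same thing. A cognitive issue can develop after surgery, and a history of non-compliance can come to light during the stay. Either judgement may be made by someone who knows how much the patient has used the device.

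If such patients are withdrawn and their data dropped, the analysed group is selected on the outcome. The result would favour the device, and a single-arm study has no control group in which the selection would show. The monitoring, quality control and safety oversight described in Sections 10.1.5 to 10.1.7 also rest with the principal investigator, so the plan describes no independent check on withdrawals.

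**Working it through.** **What the text permits**

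1. Section 7.2 applies any exclusion criterion, newly developed or newly recognised. No criterion is carved out.
2. Exclusion 2 contains an investigator-opinion test on complying with study procedures. The test is attached to listed conditions and is not an exclusion in its own right.
3. Device use is visible to staff, and nobody is blinded (Sections 4.1 and 6.3).
4. Section 7.1 points to discarding a discontinued patient's data. Sections 9.3 and 9.4 do not say that they are kept.
5. Section 8.1 leaves frequency of use to the patient. No section states whether low use may inform a withdrawal.

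Steps 1 to 3 open a route from the outcome to withdrawal. Step 4 turns a withdrawal into a missing patient.

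**Size of the effect**

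The plan has no figure to reproduce. The target of 30 was set by expected case flow (Section 9.2), and no SD, effect size or dropout rate is given. What follows is an illustration.

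Inputs:
- n = 30, from Section 9.2.
- Mean 35.4 per day, the reminder-arm figure from the cardiac surgery trial cited in Section 2.2, borrowed for scale only.
- Assumed: a gamma distribution with SD 10, 15 or 20 per day.
- Assumed worst case: the k patients removed are exactly the k lowest users.

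Removing k of n patients changes the mean by

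shift = k/(n − k) × (overall mean − mean of those removed).

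For k = 3 the multiplier is 3/27 = 1/9. The mean of the lowest three comes from 200,000 simulated trials of 30 patients.

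| Assumed SD | Mean of lowest 3 | Shift = (35.4 − that mean)/9 | New mean | Average sample SD, before and after | SD ratio |
|---|---|---|---|---|---|
| 10 | 20.7 | 1.6 | 37.0 | 9.9, 9.0 | 0.91 |
| 15 | 15.0 | 2.3 | 37.7 | 14.8, 13.8 | 0.93 |
| 20 | 10.3 | 2.8 | 38.2 | 19.7, 18.7 | 0.95 |

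As a share of the mean, 1.6/35.4 = 4.5% and 2.8/35.4 = 7.9%. With one patient removed the shift is about 0.6 to 1.0 per day; with five it is about 2.6 to 4.6.

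For consistency, with a beta distribution, an assumed mean of 50% and an assumed SD of 20 to 25 points, removing the lowest three gives 53.6% to 54.4%, a rise of about 4 points.

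For scale, the 95% half-width of a mean with n = 30 is 2.045 × SD/√30, which is 3.7, 5.6 and 7.5 per day for the three SDs. The worst-case shift with three removed is about 0.4 of that half-width in each case (1.6/3.7, 2.3/5.6, 2.8/7.5).

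**The case against.** The strongest reply is that the protocol never makes low use a reason for withdrawal. Exclusion 2 lists conditions: prior non-compliance with therapy, a psychiatric condition, a cognitive issue. Low use of the device during the stay is none of them. Section 7.2 also requires that the criterion rule out further participation, and Section 8.1 makes low use legitimate participation. This stands. A reader might infer that Section 7.2 tells investigators to remove poor users, or that it flatly contradicts Section 8.1. The documents support neither: Section 8.1 limits how Section 7.2 should be read. What remains is that a discretionary judgement about compliance is open during the stay, and no section says how use may enter it.

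A reader might also blame the no-replacement rule. That is wrong, because replacing withdrawn low users would leave the mean just as high. The bias comes from dropping their data, so the root lies in Section 7.1 and the undefined analysis set.

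On size, a truncated normal would suggest more. Cutting the lowest 10% raises the mean by 0.195 SD and reduces the SD to 0.84 of its value, or +3.5 per day with an assumed mean of 35 and SD of 18. That model puts about 2.6% of patients below zero breaths per day. A gamma distribution with the same mean and SD gives about +2.6.

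Finally, the study is exploratory, with no hypothesis in Section 9.1 and no decision threshold. That limits the consequence but does not remove a bias in the headline figure.

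**Conclusion.** The point holds as a permission in the text together with a gap in the analysis plan. Sections 7.2 and 5.2 allow withdrawals related to the behaviour that both primary endpoints measure, by someone who can see that behaviour. Section 7.1 would then remove those patients from the analysis. Where low users are the ones removed, both means move upward.

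With the lowest 3 of 30 removed, the illustration gives about +1.6 to +2.8 breaths per day (5 to 8%), an SD at about 0.91 to 0.95 of its value, and about +4 points on consistency. These figures rest on assumed distributions and SDs, a borrowed mean, an assumed number of withdrawals, and the worst case in which exactly the lowest users go. The bias is zero if the rule is never used, and zero in expectation if withdrawals are unrelated to use. The documents do not show that such withdrawals will happen. The change is still worth making, because it costs little and most of the bias disappears once the data are kept.

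**What to change.** 1. **Keep the data.** Replace the statement in Section 7.1 that a discontinued patient's data have no analytical use. State in Sections 9.3 and 9.4 that all patients who received the digital IS and started it after surgery are analysed, with device data up to the date of withdrawal in both primary summaries. Say that the days and powered-on hours in the denominators stop at that date.
2. **Make withdrawals visible.** Section 7.2 already asks for the reason. Add the specific criterion and the date for each investigator withdrawal, and report withdrawals by reason with device use beforehand.
3. **Reconcile the sections.** Sections 5.2 (exclusion 2), 7.2 and 8.1 should agree on whether low device use can inform an investigator withdrawal. The clinical grounds for withdrawal remain a matter for the investigators.

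The cost is a few sentences and two extra fields in the withdrawal record. The reported mean may be slightly lower, and some patients will contribute only part of a stay.
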